5.2.1.5 Duration of Therapy

Patients may continue on therapy until one of the following criteria applies:

- Disease progression (with the exception of pseudoprogression as described in Section 5.9),
- Intercurrent illness that prevents further administration of treatment,
- Unacceptable adverse event(s),
- Patient decides to withdraw from the study, or
- General or specific changes in the patient's condition that renders the patient unacceptable for further treatment in the judgment of the investigator.

5.2.1.6 Dose Modifications

Vorinostat should be held when \geq Grade 3 to 4 drug-related adverse experiences occur. After resolution of these adverse experiences to Grade 1 or less (or to pretreatment baseline level of toxicity) treatment with vorinostat may continue at the next lower dose (see 2.1). Once the dose has been reduced, patients must remain at the reduced dose for the remainder of the study. Patients may have their dose reduced once before being removed from the trial. Patients may only have their dose reduced to dose level 1. If grade 3 or 4 diarrhea develops despite supportive care, patients will discontinue further treatment with vorinostat.

Vorinostat in combination with other agents could cause an exacerbation of any adverse event currently known to be caused by the other agent, or the combination may result in events never previously associated with either agent.

Please see tables below for a list of adverse events experienced by patients who have been treated with vorinostat.

Experiences by Preferred Terms experienced by $\geq 10\%$ of All Patients
Overall Population - Vorinostat Patients

	Total							
	All Events				Drug-Related Events			
	All Grades		Grades 3-5		All Grades		Grades 3-5	
	n	(%)	n	(%)	n	(%)	n	(%)
Patients in population with one or more adverse events	1,744		1,744		1,744		1,744	
with no adverse events	1,701	(97.5)	1,291	(74.0)	1,561	(89.5)	957	(54.9)
	43	(2.5)	453	(26.0)	183	(10.5)	787	(45.1)
Nausea	995	(57.1)	100	(5.7)	895	(51.3)	86	(4.9)
Diarrhoea	892	(51.1)	126	(7.2)	759	(43.5)	116	(6.7)
Fatigue	821	(47.1)	221	(12.7)	700	(40.1)	188	(10.8)
Vomiting	661	(37.9)	63	(3.6)	566	(32.5)	56	(3.2)
Thrombocytopenia	630	(36.1)	443	(25.4)	537	(30.8)	372	(21.3)
Anaemia	489	(28.0)	210	(12.0)	296	(17.0)	101	(5.8)
Decreased appetite	455	(26.1)	47	(2.7)	373	(21.4)	39	(2.2)
Constipation	448	(25.7)	25	(1.4)	230	(13.2)	12	(0.7)
Neutropenia	396	(22.7)	306	(17.5)	311	(17.8)	232	(13.3)
Dyspnoea	335	(19.2)	80	(4.6)	97	(5.6)	11	(0.6)
Pyrexia	331	(19.0)	23	(1.3)	116	(6.7)	6	(0.3)
Cough	311	(17.8)	12	(0.7)	46	(2.6)	2	(0.1)
Weight decreased	284	(16.3)	14	(0.8)	213	(12.2)	12	(0.7)
Asthenia	248	(14.2)	77	(4.4)	170	(9.7)	62	(3.6)
Blood creatinine increased	227	(13.0)	6	(0.3)	170	(9.7)	3	(0.2)

Experiences by Preferred Terms experienced by $\geq 10\%$ of All Patients
Overall Population - Vorinostat Patients (Cont.)

	Total							
	All Events				Drug-Related Events			
	All Grades		Grades 3-5		All Grades		Grades 3-5	
	n	(%)	n	(%)	n	(%)	n	(%)
Anorexia	226	(13.0)	23	(1.3)	197	(11.3)	21	(1.2)
Hyperglycaemia	223	(12.8)	42	(2.4)	139	(8.0)	21	(1.2)
Leukopenia	211	(12.1)	112	(6.4)	170	(9.7)	75	(4.3)
Headache	210	(12.0)	10	(0.6)	88	(5.0)	6	(0.3)
Dizziness	207	(11.9)	14	(0.8)	108	(6.2)	8	(0.5)
Dysgeusia	203	(11.6)	2	(0.1)	186	(10.7)	2	(0.1)
Alopecia	188	(10.8)	11	(0.6)	139	(8.0)	8	(0.5)
Abdominal pain	184	(10.6)	22	(1.3)	95	(5.4)	6	(0.3)
Hypokalaemia	179	(10.3)	67	(3.8)	90	(5.2)	31	(1.8)
Back pain	177	(10.1)	24	(1.4)	19	(1.1)	2	(0.1)

Every patient is counted a single time for each applicable specific adverse event. A patient with multiple adverse events within a system organ class is counted a single time for that system organ class.

A system organ class or specific adverse event appears on this report only if its incidence in one or more of the columns is greater than or equal to the percent incidence specified in the report title, after rounding.

Only the highest reported grade of a given adverse event is counted for the individual patient.

Pembrolizumab:

AEs associated with pembrolizumab exposure, including coadministration with additional compounds, may represent an immunologic aetiology. These immune-related AEs (irAEs) may occur shortly after the first dose or several months after the last dose of pembrolizumab/combination treatment and may affect more than one body system simultaneously. Therefore, early recognition and initiation of treatment is critical to reduce complications. Based on existing clinical study data, most irAEs were reversible and could be managed with interruptions of pembrolizumab/combination treatment, administration of corticosteroids and/or other supportive care. For suspected irAEs, ensure adequate evaluation to confirm etiology or exclude other causes. Additional procedures or tests such as bronchoscopy, endoscopy, skin biopsy may be included as part of the evaluation. Dose modification and toxicity management guidelines for irAEs associated with pembrolizumab/combination treatment are provided in Table 3.

Attribution of Toxicity:

When study interventions are administered in combination, attribution of an adverse event to a single component is likely to be difficult. Therefore, while the investigator may attribute a toxicity event to the combination, to vorinostat or to pembrolizumab alone, for adverse events listed in Table 3, both interventions must be held according to the criteria in Table 3 Dose Modification and Toxicity Management Guidelines for Immune-Related Adverse Events Associated with Pembrolizumab.

Holding Study Interventions:

When study interventions are administered in combination, if the AE is considered immune-related, both interventions should be held according to recommended dose modifications.

Restarting Study Interventions:

Participants may not have any dose modifications (no change in dose or schedule) of pembrolizumab in this study, as described in Table 3.

1. If the toxicity does not resolve or the criteria for resuming treatment are not met, the participant must be discontinued from all study interventions.

2. If the toxicities do resolve and conditions are aligned with what is defined in Table 3, the combination of vorinostat and pembrolizumab may be restarted at the discretion of the investigator. In these cases where the toxicity is attributed to the combination or to vorinostat alone, re-initiation of pembrolizumab as a monotherapy may be considered at the principal investigator's discretion.

Pembrolizumab may be interrupted for situations other than treatment-related AEs such as medical / surgical events and/or unforeseen circumstances not related to study intervention. However, intervention is to be restarted within 3 weeks of the originally scheduled dose and within 42 days of the previously administered dose, unless otherwise discussed with the Sponsor. The reason for study intervention interruption is to be documented in the patient's study record.

Table 3: Dose modification and toxicity management guidelines for immune-related AEs associated with pembrolizumab monotherapy and IO Combinations

General instructions:				
irAEs	Toxicity Grade (CTCAE v5.0)	Action With Pembrolizumab	Corticosteroid and/or Other Therapies	Monitoring and Follow-up
Pneumonitis	Grade 2	Withhold	
 Administer corticosteroids (initial dose of 1 to 2 mg/kg prednisone or equivalent) followed by taper Add prophylactic antibiotics for opportunistic infections 	
 Monitor participants for signs and symptoms of pneumonitis Evaluate participants with suspected pneumonitis with radiographic imaging and initiate corticosteroid treatment
	Recurrent Grade 2, Grade 3 or 4	Permanently discontinue		

Diarrhea/Colitis	Grade 2 or 3	Withhold	
 Administer corticosteroids (initial dose of 1 to 2 mg/kg prednisone or equivalent) followed by taper 	
 Monitor participants for signs and symptoms of enterocolitis (ie, diarrhea, abdominal pain, blood or mucus in stool with or without fever) and of bowel perforation (ie, peritoneal signs and ileus)
	Recurrent Grade 3 or Grade 4	Permanently discontinue		
 Participants with \geqGrade 2 diarrhea suspecting colitis should consider GI consultation and performing endoscopy to rule out colitis Participants with diarrhea/colitis should be advised to drink liberal quantities of clear fluids. If sufficient oral fluid intake is not feasible, fluid and electrolytes should be substituted via IV infusion
AST or ALT Elevation or Increased Bilirubin	Grade 2 ^a	Withhold	
 Administer corticosteroids (initial dose of 0.5 to 1 mg/kg prednisone or equivalent) followed by taper 	
 Monitor with liver function tests (consider weekly or more frequently until liver enzyme value returned to baseline or is stable)
	Grade 3 ^b or 4 ^c	Permanently discontinue	
 Administer corticosteroids (initial dose of 1 to 2 mg/kg prednisone or equivalent) followed by taper 	
T1DM or Hyperglycemia	New onset T1DM or Grade 3 or 4 hyperglycemia associated	Withhold ^d	
 Initiate insulin replacement therapy for participants with T1DM 	
 Monitor participants for hyperglycemia or other signs and symptoms of diabetes

	with evidence of β -cell failure		
 Administer antihyperglycemic in participants with hyperglycemia 	
Hypophysitis	Grade 2	Withhold	
 Administer corticosteroids and initiate hormonal replacements as clinically indicated 	
 Monitor for signs and symptoms of hypophysitis (including hypopituitarism and adrenal insufficiency)
	Grade 3 or 4	Withhold or permanently discontinue ^d		
Hyperthyroidism	Grade 2	Continue	
 Treat with nonselective beta-blockers (eg, propranolol) or thionamides as appropriate 	
 Monitor for signs and symptoms of thyroid disorders
	Grade 3 or 4	Withhold or permanently discontinue ^d		
Hypothyroidism	Grade 2, 3 or 4	Continue	
 Initiate thyroid replacement hormones (eg, levothyroxine or liothyronine) per standard of care 	
 Monitor for signs and symptoms of thyroid disorders
Nephritis: grading according to increased creatinine or acute kidney injury	Grade 2	Withhold	
 Administer corticosteroids (prednisone 1 to 2 mg/kg or equivalent) followed by taper 	
 Monitor changes of renal function
	Grade 3 or 4	Permanently discontinue		
Neurological Toxicities	Grade 2	Withhold	
 Based on severity of AE administer corticosteroids 	
 Ensure adequate evaluation to confirm etiology and/or exclude other causes
	Grade 3 or 4	Permanently discontinue		
Myocarditis	Grade 1	Withhold		

	Grade 2, 3 or 4	Permanently discontinue	
 Based on severity of AE administer corticosteroids 	
 Ensure adequate evaluation to confirm etiology and/or exclude other causes 		
Exfoliative Dermatologic Conditions	Suspected SJS, TEN, or DRESS	Withhold	
 Based on severity of AE administer corticosteroids 	
 Ensure adequate evaluation to confirm etiology or exclude other causes 		
	Confirmed SJS, TEN, or DRESS	Permanently discontinue				
All irAEs	Persistent Grade 2	Withhold	
 Based on severity of AE administer corticosteroids 	
 Ensure adequate evaluation to confirm etiology or exclude other causes 		
	Grade 3	Withhold or discontinue based on the event ^e				
	Recurrent Grade 3 or Grade 4	Permanently discontinue				

AE(s)=adverse event(s); ALT= alanine aminotransferase; AST=aspartate aminotransferase; CTCAE=Common Terminology Criteria for Adverse Events; DRESS=Drug Rash with Eosinophilia and Systemic Symptom; GI=gastrointestinal; IO=immuno-oncology; ir=immune related; IV=intravenous; SJS=Stevens-Johnson Syndrome; T1DM=type 1 diabetes mellitus; TEN=Toxic Epidermal Necrolysis; ULN=upper limit of normal.
						

Note: Non-irAE will be managed as appropriate, following clinical practice recommendations.
						

^a AST/ALT: >3.0 to 5.0 x ULN if baseline normal; >3.0 to 5.0 x baseline, if baseline abnormal; bilirubin:>1.5 to 3.0 x ULN if baseline normal; >1.5 to 3.0 x baseline if baseline abnormal
						

^b AST/ALT: >5.0 to 20.0 x ULN, if baseline normal; >5.0 to 20.0 x baseline, if baseline abnormal; bilirubin:>3.0 to 10.0 x ULN if baseline normal; >3.0 to 10.0 x baseline if baseline abnormal
						

^c AST/ALT: >20.0 x ULN, if baseline normal; >20.0 x baseline, if baseline abnormal; bilirubin: >10.0 x ULN if baseline normal; >10.0 x baseline if baseline abnormal
						

^d The decision to withhold or permanently discontinue pembrolizumab is at the discretion of the investigator or treating physician. If control achieved or \leq Grade 2, pembrolizumab may be resumed.

^e Events that require discontinuation include, but are not limited to: encephalitis and other clinically important irAEs.

Dose modification and toxicity management of infusion-reactions related to pembrolizumab

Pembrolizumab may cause severe or life-threatening infusion-reactions including severe hypersensitivity or anaphylaxis. Signs and symptoms usually develop during or shortly after drug infusion and generally resolve completely within 24 hours of completion of infusion. Dose modification and toxicity management guidelines on pembrolizumab associated infusion reaction are provided in Table 4.

Table 4 Pembrolizumab Infusion Reaction Dose modification and Treatment Guidelines

NCI CTCAE Grade	Treatment	Premedication at Subsequent Dosing
Grade 1 Mild reaction; infusion interruption not indicated; intervention not indicated	Increase monitoring of vital signs as medically indicated until the participant is deemed medically stable in the opinion of the investigator.	None
Grade 2 Requires therapy or infusion interruption but responds promptly to symptomatic treatment (e.g., antihistamines, NSAIDs, narcotics, IV fluids); prophylactic medications indicated for ≤ 24 hrs	
Stop Infusion.
 
Additional appropriate medical therapy may include but is not limited to:
 
IV fluids Antihistamines NSAIDs Acetaminophen Narcotics
 
Increase monitoring of vital signs as medically indicated until the participant is deemed medically stable in the opinion of the investigator.
 
If symptoms resolve within 1 hour of stopping drug infusion, the infusion may be restarted at 50% of the original infusion rate (e.g. from 100 mL/hr to 50 mL/hr). Otherwise dosing will be held until
	Participant may be premedicated 1.5h (\pm 30 minutes) prior to infusion of study intervention with: Diphenhydramine 50 mg po (or equivalent dose of antihistamine). Acetaminophen 500-1000 mg po (or equivalent dose of analgesic).

	
symptoms resolve and the participant should be premedicated for the next scheduled dose.
 
Participants who develop Grade 2 toxicity despite adequate premedication should be permanently discontinued from further study drug intervention
	
Grades 3 or 4 Grade 3: Prolonged (i.e., not rapidly responsive to symptomatic medication and/or brief interruption of infusion); recurrence of symptoms following initial improvement; hospitalization indicated for other clinical sequelae (e.g., renal impairment, pulmonary infiltrates) Grade 4: Life-threatening; pressor or ventilatory support indicated	
Stop Infusion.
 
Additional appropriate medical therapy may include but is not limited to:
 
Epinephrine** IV fluids Antihistamines NSAIDs Acetaminophen Narcotics Oxygen Pressors Corticosteroids Increase monitoring of vital signs as medically indicated until the participant is deemed medically stable in the opinion of the investigator. Hospitalization may be indicated.
 
**In cases of anaphylaxis, epinephrine should be used immediately.
 
Participant is permanently discontinued from further study drug intervention.
	No subsequent dosing

Appropriate resuscitation equipment should be available at the bedside and a physician readily available during the period of drug administration.
 
For further information, please refer to the Common Terminology Criteria for Adverse Events v5.0 (CTCAE) at http://ctep.cancer.gov
		

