5.2.1.4 Supportive Care Guidelines

Note: there is an overlap in potential toxicity related to diarrhea.

If the patient has diarrhea (loose stool) = Grade 2, follow the supportive care guidelines for Vorinostat below. If the patient has diarrhea (loose stool) \ge Grade 3, follow the supportive care guidelines for Vorinostat below.

If a patient has colitis (diarrhea with abdominal pain, mucus or blood in stool) \ge Grade 2, follow the supportive care guidelines for Pembrolizumab below.

Vorinostat: Because vorinostat's dose limiting toxicities are anorexia, dehydration, diarrhea, and fatigue, patients should maintain adequate fluid and food intake. Patients will be encouraged to seek a nutritional consult, if necessary.

Treat diarrhea promptly with appropriate supportive care, including loperamide. Instruct patients to begin taking loperamide at the first signs of:

- Poorly formed or loose stool
- Occurrence of more bowel movements than usual in one day, or
- Unusually high volume of stool.

Loperamide should be taken in the following manner: 4 mg at first onset of diarrhea, then 2 mg after each unformed stool. Daily dose should not exceed 16 mg/day. Loperamide should not be taken prophylactically. Advise patients to drink plenty of clear fluids to help prevent dehydration caused by diarrhea. Avoid loperamide if there is the presence of blood or mucus in the stool or if diarrhea is accompanied by fever. If grade 3 or 4 diarrhea develops on loperamide, discontinue further treatment with vorinostat.

Pembrolizumab: Supportive care guidelines for pembrolizumab can be found in Appendix 14.5.

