	Other important medical events that may not result in death, not be life threatening, or not require hospitalization may be considered a serious adverse event when, based upon appropriate medical judgment, the event may jeopardize the subject and may require medical or surgical intervention to prevent one of the outcomes listed previously (designated above by a †).	
Duration	Record the start and stop dates of the adverse event. If less than 1 day, indicate the appropriate length of time and units	
Action taken	Did the adverse event cause pembrolizumab or vorinostat to be discontinued?	
Relationship to Pembrolizumab or Vorinostat	Did pembrolizumab or vorinostat cause the adverse event? The determination of the likelihood that pembrolizumab or vorinostat caused the adverse event will be provided by an investigator who is a qualified physician. The investigator's signed/dated initials on the source document or worksheet that supports the causality noted on the AE form, ensures that a medically qualified assessment of causality was done. This initialed document must be retained for the required regulatory time frame. The criteria below are intended as reference guidelines to assist the investigator in assessing the likelihood of a relationship between the test drug and the adverse event based upon the available information.	
	The following components are to be used to assess the relationship between pembrolizumab or vorinostat and the AE; the greater the correlation with the components and their respective elements (in number and/or intensity), the more likely pembrolizumab or vorinostat caused the adverse event (AE):	
	Exposure	Is there evidence that the subject was actually exposed to pembrolizumab or vorinostat such as: reliable history, acceptable compliance assessment (pill count, diary, etc.), expected pharmacologic effect, or measurement of drug/metabolite in bodily specimen?
	Time Course	Did the AE follow in a reasonable temporal sequence from administration of pembrolizumab or vorinostat? Is the time of onset of the AE compatible with a drug-induced effect?
	Likely Cause	Is the AE not reasonably explained by another etiology such as underlying disease, other drug(s)/vaccine(s), or other host or environmental factors

Relationship to Pembrolizumab or Vorinostat (continued)		The following components are to be used to assess the relationship between the test drug and the AE: (continued)

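### After a first Grade 3 diarrhoea that develops despite supportive care and resolves, section 5.2.1.6 stops vorinostat in one place and, in another, allows the combination to restart with no exception for that stop

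*Combined protocol and SAP*

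**What the plan says.** Two sets of instructions in 5.2.1.6 (Dose Modifications) bear on vorinostat after Grade 3 diarrhoea.

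- **First paragraph.** Vorinostat is held for drug-related Grade 3 to 4 events and may resume one level lower after recovery. Diarrhoea is treated separately: "If grade 3 or 4 diarrhea develops despite supportive care, patients will discontinue further treatment with vorinostat". That sentence does not depend on attribution or on whether the event is the first, and it offers no restart. Section 5.2.1.4 has a matching instruction: "If grade 3 or 4 diarrhea develops on loperamide, discontinue further treatment with vorinostat".
- **Attribution of Toxicity, Table 3 and Restarting Study Interventions.** The attribution paragraph allows that an event may be ascribed to the combination or to either drug alone, and then says: "for adverse events listed in Table 3, both interventions must be held according to the criteria in Table 3". The Diarrhea/Colitis row withholds treatment at Grade 2 or 3. Permanent discontinuation is reserved for "Recurrent Grade 3 or Grade 4". Item 2 under Restarting Study Interventions continues: "If the toxicities do resolve and conditions are aligned with what is defined in Table 3, the combination of vorinostat and pembrolizumab may be restarted", as the investigator chooses. It adds that pembrolizumab alone may be considered when the event is attributed to the combination or to vorinostat.

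**The concern.** For a first Grade 3 event that occurs despite supportive care and then resolves, one instruction ends vorinostat and the other lets it come back with pembrolizumab. No sentence says which applies.

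At stake is whether a patient is re-exposed to vorinostat after severe diarrhoea, which 5.2.1.4 names among that drug's dose-limiting toxicities. Reporting is affected too. Section 8.10 reports the proportion of patients with discontinuations due to adverse events, 8.8 tabulates reasons for incomplete dosing, and 8.6 tabulates violations of the treatment plan. Table 6 asks of each event: "Did the adverse event cause pembrolizumab or vorinostat to be discontinued". The same clinical course can be recorded as a vorinostat discontinuation at one site and as a hold with restart at another. Whether the restart is a treatment-plan violation depends on which instruction is taken to govern.

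**Working it through.** The plan gives no figure to reproduce here. The check follows one patient through both sets of instructions and then sizes the affected group.

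**1. The case.** Combination phase; first Grade 3 diarrhoea or colitis; develops despite supportive care; later resolves.

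**2. First paragraph.** The diarrhoea sentence comes after the general hold-and-resume rule and departs from it. Vorinostat ends, and resolution does not reopen it.

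**3. Table 3 with item 2.** Diarrhoea/colitis is a listed event, so both drugs are held whichever drug is blamed. The event is Grade 3 and not recurrent, so the row says withhold. On resolution, item 2 permits the combination, which includes vorinostat.

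**4. Where the two agree.**

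| Event | First paragraph (vorinostat) | Table 3 with item 2 | Conflict |
|---|---|---|---|
| Grade 2 | stop rule not triggered | withhold; may restart | no |
| First Grade 3, despite supportive care, resolved | stop | withhold; combination may restart | **yes** |
| Recurrent Grade 3 | stop | permanent stop | no |
| Grade 4 | stop | permanent stop | no |

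The conflict is confined to one row.

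**5. Is there a ranking elsewhere?** Section 5.2.1.4 acknowledges the overlap. It sends loose stool to the vorinostat guideline and colitis to the pembrolizumab guideline, but mentions neither Table 3 nor restarting. Neither item 1 nor item 2 refers back to the first paragraph's diarrhoea sentence.

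**6. Size.** Inputs: drug-related Grade 3-5 diarrhoea in 116 of 1,744 vorinostat patients (table in 5.2.1.6, doses not stated); 45 expansion patients in three cohorts of 15 (2.1, 8.4).

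- Rate: 116/1,744 = 0.0665.
- Expected events: 45 × 0.0665 = 2.99; 15 × 0.0665 = 1.00.
- Chance of at least one: 1 − (1 − 0.0665)^45 = 0.955; 1 − (1 − 0.0665)^15 = 0.644.
- If the rate at 100-200 mg were a quarter of this (assumption): 0.0665/4 = 0.0166; 45 × 0.0166 = 0.75; 1 − (1 − 0.0166)^45 = 0.530; 1 − (1 − 0.0166)^15 = 0.222.
- Effect of one patient on a cohort's rate of discontinuation for adverse events: 1/15 = 6.7 percentage points.

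These counts are upper figures for the affected group. The 116 include Grade 4-5 events and may include events without prior supportive care or without recovery, none of which meet the conflict. The table covers vorinostat patients; the plan gives no rate of colitis for the combination.

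**7. Dose consequence.** For a patient on 200 mg, later vorinostat is 0 mg per cycle under the stop. Under a restart it is 14 × 100 = 1,400 mg, if the next lower dose is used. That is an assumption, because item 2 names no restart dose.

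**The case against.** The strongest reply is that both instructions can be obeyed at once. The stop is mandatory and specific, while item 2 is a general permission. An investigator who restarts pembrolizumab alone breaks neither, and item 2 provides for that when the event is attributed to the combination or to vorinostat. Section 5.2.1.4 also routes loose stool of Grade 3 or higher to the guideline that contains the stop. Table 3 is titled for immune-related events, its action column concerns pembrolizumab, and a note under it leaves other events to clinical practice.

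Much of this stands: it makes the stop the better reading. It does not remove the conflict, for four reasons.

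- The priority is inferred. The design has a single-agent run-in and a combination phase, so a site could in good faith take the first paragraph as the general vorinostat rule and the later text as the combination rule.
- The attribution paragraph applies Table 3 to listed events even when vorinostat alone is blamed.
- Limiting Table 3 to immune-related events still leaves Grade 3 immune colitis in conflict, because the stop is not limited by cause.
- When the event is attributed to pembrolizumab, the only restart that item 2 names is the combination.

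A reader might infer a second conflict from footnote d of Table 3, which ends "Grade 2, pembrolizumab may be resumed", set against the first paragraph's recovery threshold: "After resolution of these adverse experiences to Grade 1 or less (or to pretreatment baseline level of toxicity) treatment with vorinostat may continue". The documents do not support that inference. Each sentence names its own drug, so both thresholds can apply together.

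In the public text the general-instructions row of Table 3 is empty. If the full table states that the vorinostat stop takes priority, the point falls away.

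**Conclusion.** The text is wrong as written, in one narrow case, and should be clarified. The stop is very probably what is intended, but item 2 carries no exception for it. Sites could therefore re-expose patients or handle identical patients differently.

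The effect is small in numbers: at most about 3 of 45 expansion patients at the protocol's vorinostat rate, and 0.75 of 45 at an assumed quarter of it. This rests on carrying a rate at unstated doses over to the combination.

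Three stronger readings are tempting but unsupported.

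- The 6.7% is not the frequency of the conflict. It covers a wider set of events.
- The efficacy results are not directly affected. Neither instruction enters the response or progression-free survival analysis in 8.9.
- The count of dose-limiting toxicities does not depend on the restart question. A related Grade 3 diarrhoea in Cycle 1 already counts under 5.2.1.3 whichever instruction is followed.

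**What to change.** In 5.2.1.6 (Dose Modifications), Restarting Study Interventions, item 2, add one sentence after the first:

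*Exception: vorinostat is not restarted after Grade 3 or 4 diarrhea that developed despite supportive care (see first paragraph of 5.2.1.6).*

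Leave item 1 and the requirement to hold both drugs under Table 3 unchanged. A broader sentence, giving vorinostat to the first paragraph and pembrolizumab to Table 3, should not be added. The first paragraph holds vorinostat only from Grade 3, so such a sentence would undo the hold on vorinostat for events such as Grade 2 pneumonitis or Grade 1 myocarditis.

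The cost is one sentence, with no extra patients, procedures or tables. The downside is that a patient whose Grade 3 immune colitis has resolved also loses vorinostat, as the first paragraph already requires. The sentence does not settle whether pembrolizumab alone may resume when the event is attributed to pembrolizumab; that is a clinical decision for the sponsor.
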